12.6.3 Vital Signs

Changes from Baseline in vital sign measurements will be summarized with descriptive statistics for each treatment group at all applicable study visits.

Version 5.0 (Amendment #4), 25NOV2019

CONFIDENTIAL

12.6.4 Concomitant Medications

All previous therapies and concomitant medications will be classified based on terminology from the World Health Organization Drug Dictionary. Previous therapies and concomitant medications data will be presented in data listings.

12.7 Interim Analyses

No interim analyses are planned.

12.8 Additional Statistical Considerations

All statistical processing will be performed using SAS® version 9.3 or higher unless otherwise stated. A SAP, describing all statistical analyses, will be provided as a separate document prior to database lock.

12.8.1 Analysis Populations

Approximately 348 subjects with moderate or severe atopic dermatitis (defined as an IGA score of 3 or 4) will be enrolled and randomized in the study. With a 2:1 randomization ratio, it is anticipated that:

- Approximately 232 subjects will be randomized to receive IDP-124 Lotion
- Approximately 116 subjects will be randomized to receive IDP-124 Vehicle Lotion

Efficacy analyses will be performed using the ITT population, the Week 6 PP population, and the Week 10 PP population. The ITT analysis set will be considered primary for the evaluation of efficacy. Safety analyses will be performed using the safety population during the treatment period (Baseline to Week 6), and during the post treatment period (Week 6 to Week 10).

All subjects who are randomized and dispensed study drug will be included in the ITT population.

All subjects who are randomized and receive at least 1 confirmed dose of study drug will be included in the safety population.

All subjects in the ITT population who complete the Week 6 visit without any major protocol violations will be included in the Week 6 PP population. The Week 6 PP population will include subjects in the ITT population who did not meet any of the following criteria:

- Violated the inclusion/exclusion criteria
- Used an interfering concomitant medication prior to Week 6
- Did not attend the Week 6 visit
- Missed more than 1 post-baseline study visit prior to Week 6

- Have not been compliant with the dosing regimen (i.e., subjects must apply 80% 120% of the expected applications of study medication during participation in the study)
- Out of visit window at the Week 6 visit by more than \pm 5 days

Subjects that discontinue from the study due to an adverse event related to study treatment or documented lack of treatment effect (and/or worsening of condition) will be included in the Week 6 PP population.

All subjects in the Week 6 PP population who complete the Week 10 visit without any major protocol violations will be included in the Week 10 PP population. Specifically, the Week 10 PP population will include subjects in the Week 6 PP population who did not meet any of the following criteria:

- Used an interfering concomitant medication between Week 6 and Week 10
- Did not attend the Week 10 visit
- Out of visit window at the Week 10 visit by more than \pm 5 days

Subjects that discontinue from the study due to an adverse event related to study treatment or documented lack of treatment effect will be included in the Week 10 PP population.

Prior to breaking the blind, other additional criteria may be added to the list to accommodate for unforeseen events that occurred during the conduct of the trial that result in noteworthy study protocol violations.

The number of subjects in each analysis population will be summarized. Reasons for study withdrawal during the blinded study will be summarized using frequencies and percentages by treatment group.

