8.3 Subject Withdrawal Criteria

When possible, subjects who discontinue from the study prior to completing the 6-week treatment period should return to the clinical center to perform the assessments scheduled for

the ET visit. If appropriate, discontinued subjects may be placed on other conventional therapy upon request or whenever clinically necessary, as determined by the physician. The End of Study source documents and all relevant data should be entered into the electronic case report form (eCRF) system at the time the subject discontinues from the study.

Reasons for subject withdrawal may include, but are not limited to, the following:

- Progression of AD, as determined by the investigator, which requires treatment with a prohibited therapy
- At the investigator's discretion for safety reasons (e.g., severe adverse reactions or unauthorized concomitant therapy)
- Subject withdrawal
- When the requirements of the protocol are not followed
- When a concomitant therapy likely to interfere with the results of the study is reported or required by the subject (the investigator will report all such information on the source documents/eCRFs and decide, in accordance with the sponsor, whether the subject is to be withdrawn)
- When a subject is lost to follow-up; the investigator (or designee) will try twice to reach the subject by telephone, email and/or text message, and will send a follow-up letter by certified mail before considering the subject as lost to follow-up. These actions will be documented on the End of Study source documents, and a copy of the follow-up letter maintained in the investigator's file
- If a subject becomes pregnant during the treatment period, the study drug will be discontinued immediately, the subject will be discontinued from the study, and the investigator will notify the sponsor. The pregnancy will be followed to term with the outcome reported to the sponsor.

9 Treatment Plan

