Descriptive statistics will be used to provide an overview of the efficacy and safety results. For categorical parameters, the number and percentage of subjects in each category will be presented. For continuous parameters, descriptive statistics will include n (number of subjects), mean, standard deviation, median, minimum, and maximum. Appropriate inferential statistics will be used for the primary, secondary, and tertiary efficacy variables.

The primary method of handling missing efficacy data will be the method of Markov Chain Monte Carlo (MCMC) multiple imputation. As a sensitivity analysis, the last observation carried forward method (LOCF) will be used (i.e., the last available on-therapy observation for a subject will be used to estimate subsequent missing data points). Additionally, a tipping point analysis will be performed for the primary endpoint. No imputations will be made for missing safety data.

A statistical analysis plan (SAP), describing all statistical analyses will be provided as a separate document. The SAP will be finalized prior to unblinding of the study treatments.

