12.8.2 Sample Size Determination

The following power calculations were computed using the IGA efficacy results from the Pimecrolimus Lotion, 1% (Elidel) NDA 21-302. Considerations were given the change in expected entry level severity of the current study. Nquery Advisor Version 7.0 with the Fisher's exact test option was used to calculate the power using a 2-sided test with an alpha of 0.05. The following table presents the efficacy estimates used in this power calculation.

Percent Dichotomized IGA Success* for Treatment Groups

	Pimecrolimus Lotion, 1%	Vehicle
Percent	23.6%	6.3%
Success		

* Success was defined as at least a 2-grade improvement from Baseline in the IGA score and an IGA score equating to "Clear" or "Almost Clear".

Overall, 232 IDP-124 Lotion treated subjects and 116 vehicle lotion treated subjects will have greater than 95% power to detect a statistically significant outcome for a 2-sided test with an alpha level of 0.05.

It was noted that the estimates extracted from the above studies are based on the LOCF method of handling missing values while the proposed Phase 3 analysis will account for missing values using multiple imputations. The power stated above sufficiently exceeds 95% which will compensate for the difference in handling of missing data.

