12.8.3 Handling of Missing Data

The primary method of handling missing efficacy data will be MCMC multiple imputation. This method does not rely on the assumption of data missing at random. Additionally, imputation will be conducted within each treatment group independently, so the pattern of missing observations in 1 treatment group cannot influence missing value estimations in another.

For each efficacy variable (IGA, EASI, pruritus severity), the following steps will be performed to impute missing data:

1. For each treatment group, create a data set containing subjects with observed values and those needing estimation by MCMC. The missing efficacy data in each data set will be filled in using the MCMC method 5 times to generate 5 data sets. The resulting data set for each treatment group will be combined into 1 complete data set for each imputation.

2. Syntax:

```
proc mi data=datain out=dataout seed=&seed. nimpute=5 <options>; where trtpn=(1 or 2); mcmc chain=multiple; var baseline week1 week2 week4 week6 week10; run;
```

- 3. Imputed data will be used to determine dichotomized success/failure values, as appropriate.
- 4. Each complete data set will be analyzed with the appropriate test (CMH, Analysis of Covariance).
- 5. CMH statistics will be normalized using the Wilson-Hilferty transformation.
- 6. The results from these analyses will be combined into a single inference using SAS PROC MIANALYZE.

A total of 6 random seeds will be needed for the multiple imputation process for the primary and secondary variables. The 6 random seeds have been prespecified by using a random number generator:

- Seed for IGA endpoints for IDP-124 = 144527508
- Seed for IGA endpoints for Vehicle = 622040939
- Seed for EASI endpoints for IDP-124 = 1706910659
- Seed for EASI endpoints for Vehicle = 2030081039
- Seed for pruritus severity endpoints for IDP-124 = 1758840189
- Seed for pruritus severity endpoints for Vehicle = 566468919

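### Subjects withdrawn for progression or lack of effect can be imputed as successes, with a higher chance per subject on active: at Week 10 on every reading, at Week 6 unless an early-termination score is used

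*Combined protocol and SAP*

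**What the plan says.** - **Withdrawal.** Section 8.3 lists "Progression of AD, as determined by the investigator, which requires treatment with a prohibited therapy" among the reasons for leaving. No expected frequency is given.
- **Analysis sets.** ITT is primary. For the per-protocol (PP) sets, Section 12.8.1 says that subjects who leave for "documented lack of treatment effect (and/or worsening of condition) will be included in the Week 6 PP population". The parallel Week 10 sentence ends "or documented lack of treatment effect will be included in the Week 10 PP population" and does not mention worsening. The synopsis has the same mismatch. Section 12.8.1 also excludes from the Week 6 PP set anyone who missed the Week 6 visit or took an interfering medication. It does not say which rule prevails.
- **Imputation.** Section 12.8.3 states: "The primary method of handling missing efficacy data will be MCMC multiple imputation". It is run separately in each arm. The variable list holds only the baseline score and the five post-baseline scores. Success or failure is derived from the imputed scores.
- **ET visit.** Section 8.3 asks discontinuing subjects to attend an ET visit where possible. Section 11.1.3 makes ET the same visit as Visit 6, with IGA, EASI and pruritus assessed. Item 15g of that section schedules Visit 7 (Week 10) only for subjects who are not at an ET visit. The windowing rules in Section 12.8.6 do not say which analysis visit an ET score belongs to.
- **Sensitivity analyses.** The opening of Section 12 describes LOCF, in which "the last available on-therapy observation for a subject will be used to estimate subsequent missing data points". Section 12.5.5 applies LOCF, a repeated-measures model on observed data, and a tipping-point analysis, all to Week 6 treatment success.

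**The concern.** When a subject leaves because the disease has progressed or the lotion is documented not to work, the reason itself says something about the outcome. The imputation model never sees it. The model combines the subject's own earlier scores with the course of same-arm subjects who have later scores. Where active subjects improve more, the same poor early record yields a success more often on active than on vehicle.

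Section 12.8.3 also claims that the method does not need data to be missing at random. The syntax shown contains no shift or pattern adjustment, so it does rest on that assumption, given the scores in the model.

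At stake are the estimated success rates in both ITT and PP, and the interpretation of the gated Week 10 endpoints (IGA success and EASI-75).

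**Working it through.** **1. The plan's own figure.** Section 12.8.2 gives success rates of 23.6% and 6.3%, and says "232 IDP-124 Lotion treated subjects and 116 vehicle lotion treated subjects will have greater than 95% power". It also says "Nquery Advisor Version 7.0 with the Fisher's exact test option was used", with "calculate the power using a 2-sided test with an alpha of 0.05". Full enumeration of the two-sided Fisher exact test for 232 vs 116 gives 99.27%; the normal approximation gives 99.28%. The claim of more than 95% is reproduced. The planned difference is 23.6 - 6.3 = 17.3 points.

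**2. Simple upper bound.** Suppose the withdrawn subjects are all true failures but are imputed at their arm's rate. With shares d_A and d_V withdrawn, inflation = d_A x 23.6 - d_V x 6.3 points.
- 10% in each arm: 0.10 x (23.6 - 6.3) = 1.73 points. Expected false successes are 232 x 0.10 x 0.236 = 5.5 on active and 116 x 0.10 x 0.063 = 0.7 on vehicle.
- 5% active, 20% vehicle: 0.05 x 23.6 - 0.20 x 6.3 = -0.08 points, a slight reversal.
- Break-even: vehicle share / active share = 23.6 / 6.3 = 3.75.

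**3. Chance of an imputed Week 6 success per withdrawn subject.** Two simulations used a normal imputation model within arm. Withdrawn subjects had no IGA improvement at their last visit, and imputed scores were rounded to whole grades. Trajectories, rounding and withdrawal shares are assumptions. Simulation A had 80% of subjects at baseline IGA 3 and 20% at IGA 4, Week 6 success of about 26% and 8%, and 6% (active) and 15% (vehicle) withdrawn. Simulation B had 85% and 15%, success tuned to 23.6% and 6.3%, and 10% withdrawn per arm.

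| Last score | A: active vs vehicle | B: active vs vehicle |
|---|---|---|
| Week 1 | 16.9% vs 4.4% | not run |
| Week 2 | 12.3% vs 3.2% | 10.5% vs 1.5% |
| Week 4 | 3.8% vs 1.6% | 5.1% vs 1.4% |

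The chance falls as more of the subject's own poor scores enter the model. In B, subjects removed at random with no post-baseline score were imputed as successes in 24.5% vs 9.4%, near their arm's rate.

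**4. Net effect on the Week 6 difference, 10% withdrawn per arm** (0.10 x difference in chance).
- A: 0.10 x (16.9 - 4.4) = 1.25; 0.10 x (12.3 - 3.2) = 0.91; 0.10 x (3.8 - 1.6) = 0.22 points (last seen Week 1, 2, 4).
- B: 0.10 x (10.5 - 1.5) = 0.90; 0.10 x (5.1 - 1.4) = 0.37 points (last seen Week 2, 4).

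**5. Net effect at 6% active and 15% vehicle, using the chances from A.**
- Week 1: 0.06 x 16.9 - 0.15 x 4.4 = 0.35 points.
- Week 2: 0.06 x 12.3 - 0.15 x 3.2 = 0.26 points.
- Week 4: 0.06 x 3.8 - 0.15 x 1.6 = -0.01 points.

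**6. Week 10.** B gives 4.6% vs 0.8% (last seen Week 2) and 2.3% vs 1.2% (last seen Week 4). If a poor ET score occupies the Week 6 slot, the Week 10 draw also conditions on it, and the chance should be lower. That case was not simulated.

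**7. Power if all such withdrawals count as failures.**
- 5% per arm: 23.6 x 0.95 = 22.4% vs 6.3 x 0.95 = 6.0%, difference 16.4 points, Fisher power 98.9%.
- 10% per arm: 21.2% vs 5.7%, difference 15.6 points, Fisher power 98.5%.

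**The case against.** The strongest reply is the ET visit. It shares the Visit 6 slot and includes the IGA, and a subject withdrawn by the investigator for progression is plausibly one who attends it. If that score serves as the Week 6 value, the subject is an observed failure and nothing is imputed at Week 6. A reader might infer that Week 6 is always imputed for these subjects; the documents do not establish that. But they do not state the mapping either, and attendance is only where possible. The reply also does not reach Week 10: the four-week follow-up after early discontinuation in the synopsis is for adverse events, not efficacy.

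Second, LOCF would usually carry a failing score forward, and the tipping-point analysis is a direct check on optimistic imputation. Both points stand for Week 6 IGA success. However, the tipping-point analysis has no stated direction or range, and Section 12.5.5 applies neither check to EASI-75, pruritus or Week 10.

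Third, a reader might infer that scores are drawn only from subjects who stayed, or that the primary result must favour the drug. The first overlooks the subject's own earlier scores. The second fails in steps 2 and 5 above, where unequal withdrawal removes or reverses the effect.

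Finally, the protocol defers detail to a separate SAP, whose text is not in the document reviewed. A rule there would settle the matter. Counting these subjects as failures is also one legitimate strategy among several; what the plan cannot do is leave the strategy unstated.

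**Conclusion.** The point holds as a gap in the handling of efficacy withdrawals, not as a threat to the trial's conclusion. A documented failure can be imputed as a success, and in every simulated case the chance per subject is higher on active. With equal withdrawal of 10% per arm, the Week 6 difference is inflated by about 0.2 to 1.25 points, with an upper bound of 1.7, against 17.3 planned. The effect shrinks to about 0.35 points or less at 6% vs 15%. At the arm rates it disappears once the vehicle share is about 3.75 times the active share, and it reverses beyond that.

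These sizes rest on assumed withdrawal shares, trajectories and rounding, none of which the documents give. Power stays above 98% in the cases computed.

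The PP conflict and the difference in wording between Week 6 and Week 10 can be read directly from Section 12.8.1. They need no simulation.

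**What to change.** - **Section 12.8.3.** Score subjects withdrawn for AD progression, worsening or documented lack of effect as non-responders for IGA success, EASI-75 and pruritus response at all visits after withdrawal. Keep multiple imputation for other reasons. State that an ET assessment is the observed value for the visit it falls in.
- **Section 12.8.1.** State that the sentence returning these subjects to the PP set prevails over the attendance and visit-window criteria. Reconcile it with the interfering-medication criterion in a way that does not drop documented failures. Use the same reason wording for Week 6 and Week 10, and align the synopsis.

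The cost is wording before unblinding. The reason for discontinuation is already recorded (Section 11.1.3, item 15g) and tabulated (Section 12.1). The downside is a slightly less favourable active success rate.

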All subjects in the ITT population who complete the Week 6 visit without any major protocol violations will be included in the Week 6 PP population. The Week 6 PP population will include subjects in the ITT population who do not meet any of the following criteria:

- Violated the inclusion/exclusion criteria;
- Used an interfering concomitant medication prior to Week 6;
- Did not attend the Week 6 visit;
- Missed more than 1 post baseline study visit prior to Week 6;
- Have not been compliant with the dosing regimen (i.e., subjects must apply 80% 120% of the expected applications of study medication during participation in the study);
- Out of visit window at the Week 6 visit by more than \pm 5 days

Subjects who discontinue from the study due to an adverse event related to study treatment or documented lack of treatment effect (and/or worsening of condition) will be included in the Week 6 PP population.

All subjects in the Week 6 PP population who complete the Week 10 visit without any major protocol violations will be included in the Week 10 PP population. Specifically, the Week 10 PP population will include subjects in the Week 6 PP population who did not meet any of the following criteria:

- Used an interfering concomitant medication between Week 6 and Week 10
- Did not attend the Week 10 visit
- Out of visit window at the Week 10 visit by more than \pm 5 days

Subjects that discontinue from the study due to an adverse event related to study treatment or documented lack of treatment effect will be included in the Week 10 PP population.

Prior to breaking the blind, other additional criteria may be added to the list to accommodate for unforeseen events that occurred during the conduct of the trial that result in noteworthy study protocol violations.

Sample Size Calculations:

Power calculations were computed using the IGA efficacy results from the Pimecrolimus Cream, 1% (Elidel) New Drug Application 21-302. Considerations were given the change in expected entry level severity of the current study. Specifically, moderate to severe subjects enrolled in pivotal Elidel studies were used for analyses. Nquery Advisor Version 7.0 with the Fisher's exact test option was used to calculate the power using a two-sided test with an alpha of 0.05. Overall, 232 IDP-124 Lotion-treated subjects and 116 Vehicle Lotion-treated subjects will have greater than 95% power to detect a statistically significant outcome for a two-sided test with an alpha level of 0.05.

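### The Week 10 per-protocol retention rule omits withdrawal for worsening, which the Week 6 rule names, so likely Week 10 failures are not protected from exclusion

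*Combined protocol and SAP*

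**What the plan says.** Section 12.8.1 and the synopsis agree with each other on both sets.

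- **Week 6 PP.** Subjects who leave because of a treatment-related adverse event (AE) are kept, as are those with "or documented lack of treatment effect (and/or worsening of condition) will be included in the" Week 6 set.
- **Week 10 PP.** This is a subset of Week 6 PP. Two of its exclusions are "Did not attend the Week 10 visit" and "Used an interfering concomitant medication between Week 6 and Week 10". The retention sentence again keeps treatment-related AEs, and then reads "or documented lack of treatment effect will be included in the Week 10 PP population". Worsening is not mentioned.

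Four other provisions bear on the point.

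- Section 8.3 lists as a reason for withdrawal "Progression of AD, as determined by the investigator, which requires treatment with a prohibited therapy". It describes an early termination visit only for subjects who leave before finishing the six weeks of treatment.
- Section 11.3.4 does not count worsening of disease as an AE, except where it leads to discontinuation or needs an intervention that the protocol prohibits.
- Section 12.8.1 makes ITT the primary set for efficacy and says efficacy will also be analysed in both PP sets.
- Section 12.8.3 handles missing efficacy data by MCMC multiple imputation within arm, using scores from Baseline to Week 10. It makes no exception for the PP sets.

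**The concern.** The two sentences do the same job, yet the later one is narrower and nothing says why. The omission falls where the words are most needed. Between Weeks 6 and 10 nobody is on study drug, so a subject who leaves for efficacy reasons in that period has most naturally relapsed. That is worsening, and it fits awkwardly under lack of treatment effect.

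Such subjects are likely failures on Week 10 IGA success and Week 10 EASI 75, the fourth and fifth endpoints in the secondary sequence. If they are excluded, membership of the Week 10 PP set depends on outcome, and the set gives too favourable a picture of persistence after treatment. A check on the ITT result should not depend on how a site happened to word a withdrawal reason.

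**Working it through.** **1. The sentences compared**

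| Reason for leaving | Named in Week 6 retention | Named in Week 10 retention |
|---|---|---|
| Treatment-related AE | yes | yes |
| Documented lack of effect | yes | yes |
| Worsening | yes | no |

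**2. Where a subject ends up, on the literal text**

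- *Leaves at Week 3, reason recorded as worsening only.* Kept in Week 6 PP. Did not attend Week 10 and has no named retention reason, so can be excluded from Week 10 PP.
- *Leaves at Week 3, reason recorded as lack of effect.* Kept in both sets.
- *Completes Week 6, relapses off drug and leaves before Week 10.* Excluded for non-attendance unless recorded as lack of effect or as a related AE.
- *As above, having started a prohibited therapy.* Also meets the interfering-medication exclusion. The plan does not say whether retention overrides it.
- *Relapses, starts such a therapy and still attends Week 10.* Has not discontinued, so the retention sentence does not apply and the medication exclusion does.

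**3. The plan's own figure.** Section 12.8.2 claims more than 95% power for 232 versus 116 subjects, 23.6% versus 6.3%, two-sided alpha 0.05, Fisher's exact test. Exact enumeration gives 99.3%, so the claim reproduces. It concerns Week 6 success in all planned subjects and does not depend on the Week 10 PP rule.

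**4. Size, by assumption.** The documents give no Week 10 success rate and no post-treatment withdrawal rate. Let *p* be the Week 10 success rate with leavers counted as failures, and *w* the share excluded, all failures. The PP rate is then *p*/(1 − *w*). For example, 0.15/0.90 = 16.7% and 0.063/0.95 = 6.6%.

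| Assumed *p*, active / vehicle | *w*, active / vehicle | PP rates | Difference if kept as failures | Difference if excluded |
|---|---|---|---|---|
| 23.6% / 6.3% | 5% / 5% | 24.8% / 6.6% | 17.3 | 18.2 |
| 23.6% / 6.3% | 20% / 10% | 29.5% / 7.0% | 17.3 | 22.5 |
| 23.6% / 6.3% | 5% / 15% | 24.8% / 7.4% | 17.3 | 17.4 |
| 15% / 6.3% | 10% / 5% | 16.7% / 6.6% | 8.7 | 10.0 |
| 15% / 6.3% | 15% / 10% | 17.6% / 7.0% | 8.7 | 10.6 |
| 15% / 6.3% | 20% / 10% | 18.8% / 7.0% | 8.7 | 11.8 |
| 15% / 6.3% | 10% / 20% | 16.7% / 7.9% | 8.7 | 8.8 |
| 15% / 6.3% | 5% / 15% | 15.8% / 7.4% | 8.7 | 8.4 |

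Both rates rise in every row. The change in the difference is *p*₁*w*₁/(1 − *w*₁) − *p*₂*w*₂/(1 − *w*₂), so its sign depends on which arm loses more. In the last row it is 0.0079 − 0.0111 = −0.0032.

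**5. Limits of these inputs.** The leavers cannot all be relapsed responders. On active, 15% still in success plus 10% leavers makes 25%, above the planned Week 6 success rate of 23.6%. On vehicle, 10% leavers exceed the 6.3% who could relapse. The scenarios therefore need some leavers who never responded, and the table shows a mechanism, not a forecast.

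**6. What the missing words alone would change.** Adding them puts the subject back in the set but does not set the outcome. Under Section 12.8.3 a missing Week 10 score is imputed from the earlier visits. A subject who was clear at Week 6, relapsed and left could often be imputed as a success. The table's comparison holds only if retained leavers are also scored as failures.

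**The case against.** The strongest reply is that the text leaves out a parenthesis; it does not exclude anyone for worsening. Two routes can keep these subjects. The Week 6 parenthesis may be only a gloss on lack of effect, in which case on-drug worsening is already covered. And worsening that leads to discontinuation is an AE under Section 11.3.4, so it is kept if assessed as related. Both routes are open, and a reader who infers that every worsening withdrawal is dropped goes too far. But neither route is secure: relapse after stopping the drug may well be assessed as unrelated, and no rule says that worsening is recorded as lack of effect.

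A second reply is that little depends on this. ITT is primary and keeps everyone, and the gated sequence is not tied to a PP set. The plan does not say which PP set serves which endpoint, so using Week 10 PP for the Week 10 endpoints is a natural inference only. The protocol also defers full statistical detail to a separate SAP, which could settle the point. All of this stands and limits the weight of the point.

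A third reply is that the bias has no established direction. This also stands. One might expect the active arm to lose more subjects because it has more responders who can relapse, but the documents give no data for that, and the arithmetic shows the difference can move either way.

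**Conclusion.** The inconsistency is certain: it appears in both places and is unexplained. Its consequence is conditional. A subject who withdraws for worsening is not protected from exclusion from Week 10 PP unless the record happens to use one of the two named reasons. Where that removes failures, the arm's PP success rate rises by a factor 1/(1 − *w*).

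The size cannot be obtained from the documents. Over the assumed scenarios the difference moves from 17.3 points to between 17.4 and 22.5, or from 8.7 points to between 8.4 and 11.8. These ranges assume that all leavers are failures and would be scored so if kept, which the plan does not currently provide.

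Two stronger inferences are not supported. The first is that the rule favours the active arm: no withdrawal rates by arm are given. The second is that it threatens the gated secondary claims: ITT is the primary efficacy set and contains these subjects. The primary analysis and the power statement are unaffected. This is a defect in a supportive analysis, worth repairing because the repair is easy.

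**What to change.** Before unblinding:

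1. Add the Week 6 parenthesis on worsening to the Week 10 retention sentence, in both Section 12.8.1 and the synopsis, so that it covers withdrawals before and after Week 6.
2. State that retention for worsening overrides the non-attendance exclusion, and also the interfering-medication exclusion when the medication was started for that worsening. Say whether the latter also applies to a subject who still attends Week 10.
3. State that, in the PP analysis, subjects retained for lack of effect or worsening count as non-successes for Week 10 IGA success and Week 10 EASI 75, and are not imputed by MCMC. Without this, step 1 could leave the PP rates unchanged or even raise them.

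The cost is one phrase in two places and two short rules. Sample size and data collection do not change. Week 10 PP success rates may come out slightly less favourable.
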